**Figure 2. Holter Monitor Electrode and Lead Placement**

## 8.0 Study Recruitment Methods

### 8.1 Recruitment of Subjects

#### 7.1.1 Pre-screen Failures

All subjects from the investigators participating in the study, and all referral sites will be prospectively documented by the study coordinator. All pre-screening subjects are those who are considered for the study but are not consented. These will be documented weekly as instructed by the CRO.

#### 7.1.2 Screen Failures

Those who are consented and do not meet all eligibility requirements will be documented weekly as instructed by the CRO. Consented screen failures may occur at the time of the run-in period, and at the time of the completion of the run-in period, prior to randomization.

#### 7.1.3 Enrollment

Those who are consented, enrolled, and undergo the ECG readings, and demonstrate the use the application of the electrodes and the ECG on the study subject.

#### 7.1.4 Enrollment Methodology

The study will include a diverse population to demonstrate the interpretability of ECG heart rhythm tracings obtained by the mobiCARE™ device in various placement locations, as compared to nominal, in a diverse population. Over 30% of the study subjects will be  $\geq 65$  years of age to assess a range of dexterity, all ethnic groups [Caucasian, Asian, African American, Hispanic, (Other (Pacific Islanders, Native American))] will be enrolled. The BMI range from low to high defined as BMI  $>35$ , will be enrolled. Male and female subjects with a minimum of 40% of the subjects being female. Varied educational levels

will be enrolled.

## 8.2 Advertising

The following advertisements will be IRB approved prior to use:

- Flyers to post in local physician's offices
- Flyers to post in local walk-in clinics
- Contents of flyers can be used for emails

The advertisement will be posters stating the study purpose, location, time required, population, subject demographics, and compensation for study participation.

## 9.0 Site Compliance

The clinical research staff will ensure compliance in the following areas and will maintain electronic documentation of compliance:

1. The most current version of the protocol, informed consent document, and HIPAA authorization.
2. All required approvals have been obtained at each site.
3. All subject information; such as name code, subject number and subject name list will be secured in the research department with only dedicated research personnel having access to the information.
4. Electronic data will be entered in the 21 CFR 11 compliant EDC database.
5. The research staff will be trained and have an understanding of all protocol requirements to ensure that investigators conduct the study appropriately.
6. Noncompliance with the protocol will be reported to the site PI by the CRO and promptly addressed.

## 10.0 Study Timelines and Data Collection

### 10.1 Duration of Subject's Participation

Subjects who consent to this study will participate for the following duration: One (1) day, for an estimated duration of one (1) hour.

### 10.2 Duration of Enrollment Period

The estimated enrollment phase is up to four (4) weeks.

### 10.3 Projected Completion Date

The anticipated completion date for the study enrollment, data analysis, report preparation is one (1) to three (3) months after first subject is enrolled.

### 10.4 Primary and Secondary Objectives

#### 9.4.1 Primary Objective

The primary objective is to quantify the placement accuracy requirements (i.e., cm/in offset may be tolerated from the nominal placement position) needed to ensure appropriate device performance including heart rhythm interpretability and provide rationale to support that such placement accuracy is adequate.

#### 9.4.2 Secondary Objectives

The secondary objectives are to:

1. Demonstrate that the device meets the placement accuracy requirements when in normal use, and
2. Identify if there are any factors that may impact the heart rhythm interpretive accuracy; such as, age, sex, educational level, body size/BMI, and dexterity.

## 10.5 Primary Endpoints and Secondary Endpoints

### 10.5.1 Primary Endpoint

Evaluation of the ECG signal at the nominal location and in up to three (3) additional standardized locations in each subject to determine if the signal is interpretable. The term “interpretable” is defined as follows: An independent cardiologist is able to identify the ECG rhythm in each location when compared to the ECG rhythm measured in the nominal position of the mobiCARE™ ECG Monitoring System described in the Instructions for Use. ECG rhythm data will be collected for up to two (2) minutes while the patient ambulates.

The simultaneous Holter Monitor will be evaluated at the same time points to have a point of reference for the mobiCARE™ system in the case that changes in the rhythm are noted during the study.

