Primary Objective	The primary objective is to quantify the placement accuracy requirements (i.e., how many cm/in. offset may be tolerated from the nominal placement position) needed to ensure appropriate device performance including heart rhythm interpretability and provide rationale to support that such placement accuracy is adequate.
Secondary Objective	The secondary objectives are to: 1. Demonstrate that the device meets the placement accuracy requirements when in normal use, and 2. Identify if there are factors that may impact the placement accuracy and subsequent heart rhythm identification such as age, sex, educational level, BMI, and dexterity.
Primary Endpoint	Evaluation of the ECG signal at the nominal location and in up to three (3) additional standardized locations in each subject to determine if the signal is interpretable. The term “interpretable” is defined as follows: An independent

	
cardiologist is able to identify the ECG rhythm in each location when compared to the ECG rhythm measured in the nominal position of the mobiCARE™ ECG Monitoring System described in the Instructions for Use. ECG rhythm data will be collected for up to two (2) minutes while the patient ambulates.
 
The simultaneous Holter Monitor will be evaluated at the same time points to have a point of reference for the mobiCARE™ system in the case that changes in the rhythm are noted during the study.

Secondary Endpoints (Informational Only)	
 
1. Presence of artifact graded as 1=none, 2=minor (cardiac rhythm is interpretable), or 3=major (cardiac rhythm is not interpretable by the independent cardiologist).
 
2. ECG Morphology measurements: P wave amplitude, QRS amplitude, QRS duration.
 
3. Limited Human Factors Evaluation Measures (n=15): 
 
A. Initial Healthcare practitioner (HCP) placement according to IFU (correct or incorrect placement when referring to the IFU)
 
B. User demonstrates ability to change electrodes (successful or not successful)
 
C. Observe user to determine sufficient dexterity for user to perform the task
 
D. Observe user electrode placement according to skin markings to determine if electrodes are correctly placed.
 
 
 

Participation Duration	Each subject will participate in this study for one (1) visit, for approximately 30 to 60 minutes.

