### 10.5.2 Secondary Endpoints – Informational Only

1. Presence of artifact graded as 1=none, 2=minor (cardiac rhythm is interpretable), or 3=major (cardiac rhythm is not interpretable by the independent cardiologist).
2. ECG Morphology measurements: P wave amplitude, QRS amplitude, QRS duration.
3. Limited Human Factors Evaluation Measures (n=15):
  - A. Initial HCP placement according to IFU (correct or incorrect placement when referring to the IFU)
  - B. User demonstrates ability to change electrodes (successful or not successful)
  - C. Observe user to determine sufficient dexterity for user to perform the task
  - D. Observe user electrode placement according to skin markings to determine if electrodes are correctly placed.

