## 11.0 Statistical Considerations

### 11.1 Introduction

Each subject will have the mobiCARE™ ECG measured at the nominal position and at 3 pre-specified alternate locations. For each location, the ECG signal will be read and classified as interpretable or not interpretable. The reading from the mobiCARE™ nominal position will serve as the comparator reading for the alternate mobiCARE™ locations. The primary endpoint analysis is the comparison of each mobiCARE™ alternate location to the nominal position.

The Holter monitor will be used as a method to verify the subjects heart rhythm during simultaneous recordings of mobiCARE™ heart rhythm data at the prespecified measurement locations on the precordium.

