### 11.2 Analysis of Primary Endpoint

The primary endpoint will be analyzed using an asymptotic non-inferiority test for the difference in interpretability of the ECG signal between two correlated proportions. The test is described in the references and discussed in references. The null and alternative hypotheses are

$$H_0: P_A - P_N \leq -M_{NI} \text{ and } H_A: P_A - P_N > -M_{NI}$$

where  $P_N$  and  $P_A$  are the proportions of measurements with interpretable ECG results at the nominal position and each alternative location, respectively, and  $M_{NI}$  is the positive non-inferiority margin. This one-sided test will be performed with type I error rate  $\alpha = 0.025$  and non-inferiority margin  $M_{NI} = 0.20$ . The test will be repeated for each alternative location, comparing it to the nominal position. No adjustment will be made for multiple comparisons.

Uninterpretable ECG at one location does not constitute a failure for that subject.

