### 11.3 Sample Size Calculation

The required sample size was computed using proc power in SAS v9.4 software for a Farrington-Manning non-inferiority test of the difference of two independent proportions. A sample size of 37 is required based on the following assumptions:

- Type I error rate  $\alpha = 0.025$
- Non-inferiority margin  $M_{NI} = 0.20$
- 80% power
- Assumed proportions of subjects with interpretable ECG signal:
  - Nominal placement: 95%
  - Alternate placement: 94%

To allow for possible 10% drop-out, a sample size of 44 will be used.

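### The stated definition of 'interpretable' is relative to the nominal tracing, so read literally the nominal position cannot fail, although P_N is an estimated proportion planned at 95%

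*Combined protocol and SAP*

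**What the plan says.** The primary endpoint in 10.5.1 is "Evaluation of the ECG signal at the nominal location and in up to three (3) additional standardized locations in each subject", so nominal is itself one of the positions scored. The definition of the score follows: "An independent cardiologist is able to identify the ECG rhythm in each location when compared to the ECG rhythm measured in the nominal position". The synopsis (1.0) repeats it: "cardiologist is able to identify the ECG rhythm in each location when compared to the ECG rhythm measured in the nominal position".

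The statistical section treats the score as a separate yes/no result for each position. In 11.1: "For each location, the ECG signal will be read and classified as interpretable or not interpretable". The same section says that the nominal reading "will serve as the comparator reading for the alternate" positions. In 11.2, P_N and P_A "are the proportions of measurements with interpretable ECG results at the nominal position and each alternative location", and the tested quantity is P_A − P_N against a margin of 0.20 at one-sided 0.025. Section 11.3 plans "Nominal placement: 95" per cent, against 94% for the alternate.

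Four further places bear on the point:
- 11.2 closes by saying that an unreadable position does not make the subject a failure.
- 11.5.2, item 3E, asks whether the signal is still interpretable after the user has refitted the device, with no paired tracing mentioned.
- 12.3.1 gives the reader tracings that are anonymized and in randomized order, without saying whether they are read one at a time.
- 10.5.2 grades artifact as major when "cardiac rhythm is not interpretable by the independent cardiologist".

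**The concern.** A definition that refers to the nominal rhythm works, at most, for the alternates. For nominal it is a comparison of a tracing with itself, which cannot fail. Yet 11.2 estimates P_N from data, and 11.3 expects about 5% of nominal tracings to fail. The stated rule and the primary test therefore do not fit together.

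The definition also ties each alternate's score to the subject's nominal tracing and does not say what happens when that tracing is unreadable. Under stand-alone scoring, a subject with an unreadable nominal and a readable alternate counts in the alternate's favour. If the alternate needs a readable reference, the subject does not. This score is the whole of the only tested endpoint, so a reader following 10.5.1 and a reader following 11.1 could score the same tracings differently.

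**Working it through.** **Inputs.** From 11.2 and 11.3: P_N = 0.95, P_A = 0.94, margin M = 0.20, one-sided α = 0.025, 80% power, n = 37, and 44 with drop-out. The overlap of failures within a subject is not given and is varied below.

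**The plan's own figure.** Farrington-Manning for two independent proportions, with restricted estimates 0.974 and 0.774 under the null:
- s0 = √(0.974×0.026 + 0.774×0.226) = 0.447
- s1 = √(0.95×0.05 + 0.94×0.06) = 0.322
- n = [(1.960×0.447 + 0.842×0.322)/(0.20 − 0.01)]² = 36.53 before rounding of intermediate values, so 37, with power 80.6%.

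The stated 37 is reproduced.

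**How often the gap would arise.** P(at least one unreadable nominal) = 1 − 0.95^37 = 0.850, and 1 − 0.95^44 = 0.895.

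**One subject, three scorings.** The planned paired test was implemented as a restricted-likelihood score test. Let b be the losses (nominal readable, alternate not), c the gains (the reverse), and q the restricted estimate of the gain rate:

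z = [(c − b)/n + M] / √[(2q + M − M²)/n], pass if z > 1.960.

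With no gains in these examples q = 0, so at n = 37 with b = 3: z = (0.20 − 3/37)/√(0.16/37) = 1.808.

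| Tracings | Stand-alone | Alternate failed when nominal unreadable | Pair excluded |
|---|---|---|---|
| n = 37, 3 losses, 1 gain | 2.048 (pass) | 1.808 (fail) | 1.750 (fail) |
| n = 44, 4 losses, 1 gain | 2.036 (pass) | 1.809 (fail) | 1.754 (fail) |

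These are boundary cases. At n = 37 with 2 losses and 1 gain, all three scorings pass (2.44, 2.22, 2.17). With 4 losses and 1 gain, stand-alone scoring already fails (1.66).

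**How often the verdict differs.** Let p00 be the probability that both readings fail. The loss rate is 0.06 − p00 and the gain rate 0.05 − p00. Power comes from exact enumeration. Failing the alternate sets the gains to zero and leaves the losses unchanged. The largest number of losses that still passes never falls as gains rise (at n = 37: 2 with no gains, 3 with one). Recoding therefore cannot turn a fail into a pass, and the difference in power is the probability of a different verdict.

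| Overlap (assumed) | p00 | n = 37: stand-alone − alternate failed | n = 44: stand-alone − alternate failed |
|---|---|---|---|
| Independent | 0.003 | 83.3 − 64.6 = 18.7% | 90.2 − 75.9 = 14.3% |
| Correlation 0.3 | 0.0185 | 89.7 − 80.3 = 9.4% | 94.9 − 89.1 = 5.8% |
| Mid overlap (correlation 0.45) | 0.0265 | 92.7 − 87.4 = 5.3% | 96.9 − 94.1 = 2.8% |
| Full overlap | 0.05 | 0 | 0 |

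Excluding the pair gives power within about 1.5 percentage points of failing the alternate in every row. Stand-alone power is above 80% in every row.

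**The case against.** The strongest reply is that stand-alone scoring is already the evident intent. Section 11.1 classifies each position. The paired test in 11.2 is built to use pairs in which nominal fails and the alternate passes, and 11.2's closing sentence weighs against penalising a subject for one unreadable position. Item 3E of 11.5.2 uses the term without a paired tracing, and identifying the rhythm is a usable criterion for nominal once the comparison is set aside. All of this stands as evidence of intent. It does not repair the definition, which is introduced expressly as such and retains the comparison. Nor do the artifact grades: they are secondary, informational, and refer back to the same term.

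Two further objections hold in part. Section 11.4 says that the practitioner sees the signal when fitting the nominal position, so unreadable nominal tracings may be rarer than 5%. But 95% is the plan's own figure, and a check at fitting does not exclude failure while walking. Also, the reference to the nominal rhythm may be a deliberate agreement requirement, and a definition that simply dropped it would be more lenient to the device. That is a fair point, and agreement should be kept as a reported result.

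A reader might infer that the trial is underpowered or that N = 37 is wrong. The documents do not support this: the lower powers belong to scoring rules that the plan does not state. A reader might also infer that 12.3.1 contradicts 10.5.1. It does not, because anonymized and randomized tracings could still be reviewed in pairs; the section only leaves the mode of reading open.

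**Conclusion.** The point holds as a conflict between a stated definition and the primary test. It should be fixed before any tracing is read, because a rule chosen afterwards could decide the result. It does not show an error in the sample size or in the test.

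The practical effect depends on two things that the plan does not give: the rule for an alternate whose nominal tracing is unreadable, and the within-subject overlap of failures. Independence is the worst case shown; since the plan itself uses a test for correlated proportions, some overlap is plausible and the effect would then be smaller.

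**What to change.** In 10.5.1 and the synopsis, define a tracing as interpretable if the reader, viewing that tracing alone and blinded to its position and to the subject's other tracings, can identify the rhythm. Say that the rule applies identically to nominal and to all alternates, and that this score feeds both P_N and P_A. In 12.3.1, state that the randomized tracings are read singly.

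Report rhythm agreement with nominal, and with the simultaneous Holter as in 11.5.1, per position as a separate supportive result. The agreement element of the present definition is then kept.

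The cost is protocol wording and a reader worksheet, with no new subjects, readers or recordings. The downside is that a readable tracing whose rhythm is misnamed counts as interpretable in the primary analysis and shows only in the agreement tables.

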### 10.5.2 Secondary Endpoints – Informational Only

1. Presence of artifact graded as 1=none, 2=minor (cardiac rhythm is interpretable), or 3=major (cardiac rhythm is not interpretable by the independent cardiologist).
2. ECG Morphology measurements: P wave amplitude, QRS amplitude, QRS duration.
3. Limited Human Factors Evaluation Measures (n=15):
  - A. Initial HCP placement according to IFU (correct or incorrect placement when referring to the IFU)
  - B. User demonstrates ability to change electrodes (successful or not successful)
  - C. Observe user to determine sufficient dexterity for user to perform the task
  - D. Observe user electrode placement according to skin markings to determine if electrodes are correctly placed.

## 11.0 Study Procedures

**Table 2: Schedule of Assessment**

Visit	Prior to the FSFV	Day of Subject's Study Visit	Study Subject Termination
Assessment			
Train Site on mobiCARE™ device placement and all Study Requirements	X		
Written informed consent		X	
Demographics and medical history		X	
Confirm eligibility criteria		X	X
Place Holter Monitor on Study Subject		X	
Observe HCP placing mobiCARE™ device on subject		X	
Observe subject ambulating, record ECG for $\geq 1$ minute		X	
Observe for SAEs / AEs / UADEs			X
Subject is terminated after all data are collected			X
Compensation Provided			X

## 11.0 Statistical Considerations

### 11.1 Introduction

Each subject will have the mobiCARE™ ECG measured at the nominal position and at 3 pre-specified alternate locations. For each location, the ECG signal will be read and classified as interpretable or not interpretable. The reading from the mobiCARE™ nominal position will serve as the comparator reading for the alternate mobiCARE™ locations. The primary endpoint analysis is the comparison of each mobiCARE™ alternate location to the nominal position.

The Holter monitor will be used as a method to verify the subjects heart rhythm during simultaneous recordings of mobiCARE™ heart rhythm data at the prespecified measurement locations on the precordium.

### 11.2 Analysis of Primary Endpoint

The primary endpoint will be analyzed using an asymptotic non-inferiority test for the difference in interpretability of the ECG signal between two correlated proportions. The test is described in the references and discussed in references. The null and alternative hypotheses are

$$H_0: P_A - P_N \leq -M_{NI} \text{ and } H_A: P_A - P_N > -M_{NI}$$

where  $P_N$  and  $P_A$  are the proportions of measurements with interpretable ECG results at the nominal position and each alternative location, respectively, and  $M_{NI}$  is the positive non-inferiority margin. This one-sided test will be performed with type I error rate  $\alpha = 0.025$  and non-inferiority margin  $M_{NI} = 0.20$ . The test will be repeated for each alternative location, comparing it to the nominal position. No adjustment will be made for multiple comparisons.

Uninterpretable ECG at one location does not constitute a failure for that subject.

### 11.3 Sample Size Calculation

The required sample size was computed using proc power in SAS v9.4 software for a Farrington-Manning non-inferiority test of the difference of two independent proportions. A sample size of 37 is required based on the following assumptions:

- Type I error rate  $\alpha = 0.025$
- Non-inferiority margin  $M_{NI} = 0.20$
- 80% power
- Assumed proportions of subjects with interpretable ECG signal:
  - Nominal placement: 95%
  - Alternate placement: 94%

To allow for possible 10% drop-out, a sample size of 44 will be used.

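### Section 11.3 takes its 37 subjects and 80% power from an independent-groups calculation although the planned test is paired, and 44 does not follow from 37 with 10% drop-out (minor; no sample size changes)

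*Combined protocol and SAP*

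**What the plan says.** Section 11.1 has every subject measured "at the nominal position and at 3 pre-specified alternate locations", and states: "The primary endpoint analysis is the comparison of each mobiCARE™ alternate location to the nominal position". Section 11.2 analyses this with an "asymptotic non-inferiority test for the difference in interpretability of the ECG signal between two correlated proportions", one-sided at 0.025 with a margin of 0.20. It adds: "The test will be repeated for each alternative location, comparing it to the nominal position" and "No adjustment will be made for multiple comparisons".

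Section 11.3 computes the sample size "for a Farrington-Manning non-inferiority test of the difference of two independent proportions". Its inputs are alpha 0.025, margin 0.20, 80% power, and interpretable proportions of 95% (nominal) and 94% (alternate). The result is 37. It then says: "To allow for possible 10% drop-out, a sample size of 44 will be used".

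Section 5.3 sets a minimum of 37 subjects analysed and a ceiling of 50 enrolled. Neither section gives a correlation between positions or a discordance rate.

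**The concern.** The power of a paired test depends on how often the two readings in one subject disagree. An independent-groups formula has no such input, so the 80% in section 11.3 is the power of a different design: two separate groups of 37. Here 37 is used as a number of pairs. From the protocol alone a reader cannot tell whether the mismatch hides a shortfall or a surplus.

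The drop-out sentence raises a second, smaller question, because the stated allowance and the stated total do not agree. At stake is whether the sample-size section describes the analysis that will be run and the number that will be enrolled.

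**Working it through.** **Inputs.** From sections 11.2 and 11.3: nominal 0.95, alternate 0.94, margin M = 0.20, one-sided alpha 0.025 (z = 1.960), power 80% (z = 0.842), drop-out 10%. From section 5.3: minimum 37, maximum 50. Assumed, because the documents do not give them: the discordance, and the exact form of the paired test. Section 11.2 calls the test asymptotic and points to a reference; I use the restricted-maximum-likelihood score form.

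**1. The plan's own figure.** Farrington-Manning, per group:

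n = [(1.960·s0 + 0.842·s1) / (0.94 − 0.95 + 0.20)]²

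The restricted estimates under the null are 0.974 and 0.774, so s0 = √(0.974·0.026 + 0.774·0.226) = 0.447. The alternative gives s1 = √(0.95·0.05 + 0.94·0.06) = 0.322. Then n = 36.5, so 37 per group. The stated 37 reproduces as an independent-groups figure.

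**2. Feasible discordance.** Let p10 be the proportion interpretable at nominal only and p01 the proportion interpretable at the alternate only. The rates 95% and 94% fix p10 = p01 + 0.01. Since p01 cannot exceed 1 − 0.95 = 0.05, the range of p10/p01 is 0.01/0 to 0.06/0.05. This corresponds to correlations from 0.91 down to −0.06. Zero correlation is 0.057/0.047.

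**3. Exact power of the paired score test.** With b subjects interpretable at nominal only and c at the alternate only, the statistic is

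z = (c − b + nM) / √[n(2q + M − M²)]

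Here q is the restricted estimate of p01. Trinomial probabilities are summed over all (b, c) with z ≥ 1.960.

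| p10/p01 | Correlation | n=37 | n=39 | n=44 |
|---|---|---|---|---|
| 0.01/0 | 0.91 | 99.4% | 99.3% | 99.9% |
| 0.03/0.02 | 0.52 | 94.0% | 93.6% | 97.6% |
| 0.057/0.047 | 0 | 83.3% | 85.0% | 90.2% |
| 0.06/0.05 | −0.06 | 82.1% | 84.0% | 89.2% |

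The column n = 39 is 44 less 10% (44 × 0.9 = 39.6, rounded down). The lowest value at any n from 37 to 50 is 81.4%, at n = 38.

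**4. Asymptotic paired formula.** This is the like-for-like comparison with the plan's asymptotic method:

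n = [(1.960·√(2q + M − M²) + 0.842·√(p10 + p01 − 0.01²)) / 0.19]²

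- Discordance 0.01/0: 20.9, so 21 pairs.
- Discordance 0.03/0.02: 28.5, so 29 pairs.
- Zero correlation: q = 0.0222, square roots 0.452 and 0.322, n = 37.1, so 38 pairs. Power at 37 is 79.9%.
- Most negative correlation: n = 38.1, so 39 pairs. Power at 37 is 78.6%.

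**5. Drop-out.** 37/0.9 = 41.1, so 42; check: 42 × 0.9 = 37.8. The stated 44 corresponds to 1 − 37/44 = 15.9%.

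**6. Dependence on the assumed rates.** As an illustration (these rates are not in the documents), keep nominal at 95% and correlation at zero. If the true alternate rate were 92%, exact power would be 69% at n = 37 and 78% at n = 44; at 90% it would be 54% and 63%.

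**The case against.** The strongest reply is that nothing material turns on this. Section 11.3 names its method openly. At the assumed rates the exact paired power exceeds 80% at 37 for every feasible discordance, and any positive correlation, which is plausible for readings in one subject, adds to it. The gap between 42 and 44 is two subjects, on the over-recruiting side, and lies within the limits of section 5.3. All of this stands, and it is why the point is minor.

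What remains is that the stated power is not the power of the planned test, and that the total does not follow from the stated allowance. Nor is the surplus unconditional: it rests on exact power, an assumed test form, and 95% versus 94%.

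A reader might go further and infer that the study is underpowered because all three alternate locations must succeed together, or that the unadjusted testing inflates a joint claim. The documents do not support this. Sections 11.1 and 11.2 define a separate comparison of each location with nominal and disclose that no adjustment is made. Section 9.4.1 says "The primary objective is to quantify the placement accuracy requirements", and neither it nor any other section makes success at all three locations a condition. A figure for all-three power would describe a claim the plan does not make, under a dependence model it does not give.

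**Conclusion.** Minor, but wrong as written in two places. First, section 11.3 reports 37 and 80% power for two independent groups although the analysis is paired. Second, 44 does not follow from 37 with 10% drop-out; the result is 42.

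There is no shortfall per location in exact power: 82% to 99% at 37, 84% to 99% at 39, and 89% to over 99% at 44. This rests on the 95% and 94% rates, the restricted-maximum-likelihood paired score test, and the full feasible discordance range. On the asymptotic formula, 37 pairs miss 80% by at most 1.4 percentage points (80 − 78.6), and only when the correlation is zero or slightly negative. The 39 pairs left from 44 after 10% loss are enough on either basis. The conclusion does not extend to a lower true alternate rate.

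**What to change.** In section 11.3, replace the independent-proportions calculation with one for the paired test in section 11.2, rerun by the sponsor's statistician. State beside it the 95% and 94% rates, the form of the test, whether power is exact or asymptotic, and the discordance range assumed. If the rerun confirms the figures above, the text could read: 'At 95% versus 94%, exact power of the paired score test for each location is 82% to 99% with 37 evaluable subjects and 89% to over 99% with 44, for discordance (nominal only/alternate only) from 0.06/0.05 to 0.01/0.'

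For drop-out, either keep 44 and state that it allows about 16%, or keep 10% and state 42. With 42 enrolled and 10% lost, 37 remain, where the asymptotic power is just under 80% at zero correlation; keeping 44 avoids that.

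Optionally, add one sentence to section 11.2 that conclusions and type I error control are for each location separately.

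The cost is wording and one rerun. No extra patients are needed, and section 5.3 is unchanged.
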